7.2 Documentation of non-serious AEs or SARs

For non-serious AEs or SARs, documentation must begin from day 1 of study treatment and continue through the 30 day follow-up period after treatment is discontinued, in this case the second planned FLT-PET MRI scan.

Collected information should be recorded in the Case Report Forms (CRF) for that patient. Please include a description of the event, its severity or toxicity grade, onset and resolved dates (if applicable), and the relationship to the study drug. Documentation should occur at least monthly.

7.3 SAEs or Serious SARs

7.3.1 Timing

After informed consent but prior to initiation of study medications/radiotracer administration, only SAEs caused by a protocol-mandated intervention will be collected (e.g. SAEs related to invasive procedures such as biopsies, medication washout).

For any other experience or condition that meets the definition of an SAE or a serious SAR, recording of the event must begin from day 1 of study treatment and continue through the 30 day follow-up period after treatment is discontinued, in this case the second planned FLT-PET MRI scan.

7.3.2 Documentation and Notification

SAEs or Serious SARs must be recorded in the SAE console within Oncore™ for that patient within 24 hours of learning of its occurrence. Additionally, the NCCN Project Manager must also be notified via email of all SAEs within 24 hours of learning of its occurrence.

7.3.3 Reporting

IRB Reporting Requirements:

UNC:

UNC will submit an aggregated list of all SAEs to the UNC IRB annually at the time of study renewal according to the UNC IRB policies and procedures.

The UNC-IRB will be notified of all SAEs that qualify as an Unanticipated Problem as per the UNC IRB Policies using the IRB's web-based reporting system (see section 9.5.3) within 7 days of the Investigator becoming aware of the problem.

Pregnancy

Pregnancies and suspected pregnancies (including a positive pregnancy test regardless of age or disease state) of a female subject occurring while the subject is on study should be recorded as SAEs. The patient is to be discontinued immediately from the study. The female subject should be referred to an obstetrician-gynecologist, preferably one experienced in reproductive toxicity for further evaluation and counseling.

The Investigator will follow the female subject until completion of the pregnancy, and must document the outcome of the pregnancy (either normal or abnormal outcome) and report the condition of the fetus or newborn to the UCCN Project Manager. If the outcome of the pregnancy was abnormal (e.g., spontaneous or therapeutic abortion), the Investigator should report the abnormal outcome as an AE. If the abnormal outcome meets any of the serious criteria, it must be reported as an SAE.

FDA Expedited Reporting requirements for studies conducted under an IND:
If an investigator deems that an event is both a serious SAR AND unexpected, it must also (in addition to Oncore) be recorded on the MedWatch Form 3500A as per 21 CFR 312.32. Unexpected adverse events or adverse reaction refers to an event or reaction that is not listed in the investigator's brochure or is not listed at the specificity or severity that has been observed; or if an investigator's brochure is not

required or available, is not consistent with the risk information described in the general investigation plan or elsewhere in the current IND application.

The MedWatch form should be faxed to the UNCCN Project Manager at [contact] (or emailed, with address provided at the Start up Meeting (SIM)) along with supporting documentation defining the event and causality. The UNCCN Project Manager will then send the report to the Funding Source.

Once the UNC Principal Investigator determines an event is a serious SAR AND unexpected, the MedWatch 3500A form will be submitted to the FDA by the UNCCN Project Manager. If the event is serious, unexpected and considered to be possibly-, probably- or definitely-related to the study treatment, the UCCN Project Manager will inform the Regulatory Associate at UNC who will be responsible for submitting the SAR to the IND. All IND safety reports must be submitted on Form 3500A and be accompanied by Form 1571. The FDA must be notified of any unexpected or life-threatening suspected adverse reactions as soon as possible, but no later than 7 calendar days of learning of the event.

The UNCCN Project Manager will also be responsible for informing each Affiliate site of all serious and unexpected SARs reported to the FDA via fax as soon as possible.

7.4 Data and Safety Monitoring Plan

The Principal Investigator will provide continuous monitoring of patient safety in this trial.

Meetings/teleconferences will be held at a frequency dependent on study accrual, and in consultation with the study Biostatistician. These meetings will include the investigators as well as protocol nurses, clinical research associates, regulatory associates, data managers, biostatisticians, and any other relevant personnel the principal investigators may deem appropriate. At these meetings, the research team will discuss all issues relevant to study progress, including enrollment, safety, regulatory, data collection, etc.

The team will produce summaries or minutes of these meetings. These summaries will be available for inspection when requested by any of the regulatory bodies charged with the safety of human subjects and the integrity of data including, but not limited to, the oversight (Office of Human Research Ethics (OHRE) Biomedical IRB, the Oncology Protocol Review Committee (PRC) or the North Carolina TraCS Institute Data and Safety Monitoring Board (DSMB).

The UNC LCCC Data and Safety Monitoring Committee (DSMC) will review the study on a regular (quarterly to annually) basis, with the frequency of review based on risk and complexity as determined by the UNC Protocol Review Committee. The UNC PI will be responsible for submitting the following

information for review: 1) safety and accrual data including the number of patients treated; 2) significant developments reported in the literature that may affect the safety of participants or the ethics of the study; 3) preliminary response data; and 4) summaries of team meetings that have occurred since the last report. Findings of the DSMC review will be disseminated by memo to the UNC PI, PRC, and the UNC IRB and DSMB.

8.0 STATISTICAL CONSIDERATIONS

8.1 Study Design

This is a non-randomized, prospective pilot study exploring the use of FLT-PET-MRI in the evaluation of allogeneic patients after bone marrow transplants to potentially predict engraftment success and the development of graft versus host disease. A total of 15 patients who have undergone bone marrow transplantation will receive FLT-PET-MRI imaging, 3 autologous and 12 allogenic recipients will be recruited. The 3 autologous patients are included as a comparator arm to help elucidate how much of the FLT signal in allogeneic HSCT patients is related to allo-antigen driven T cell proliferation and therefore unique to the allogeneic setting.

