1.0 BACKGROUND AND RATIONALE

1.1 Study Synopsis

This is a non-randomized, prospective pilot study exploring the use of fluorothymidine (FLT)-PET-MRI in the evaluation of allogeneic bone marrow transplant patients to potentially predict engraftment success, malignancy relapse, and the development of graft versus host. A total of 12 patients who have undergone allogeneic bone marrow transplantation will undergo FLT-PET-MRI imaging on two separate occasions. The first scan will occur immediately after initial neutrophil count recovery on day +25. The second scan will occur on transplant day +60 by which time stable count recovery should have occurred. The findings on the first scan will be correlated with clinical outcomes and pathological results on transplant day +35, and the findings on the second scan will be correlated with clinical outcomes and pathological results on day +100. The day +35 and +100 time points were chosen because allogeneic transplant patients at our institution undergo a restaging bone marrow biopsy and aspirate with donor/recipient chimerism studies around these days as part of our usual standard of care. In addition to the 12 allogeneic transplant patients, 3 patients undergoing autologous stem cell transplant will also be imaged at the same two time points in order to determine how much of the FLT signal observed after allogeneic transplant is unique to that population and the result of allo-antigen driven T cell expansion.

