appeared to be more heterogeneous in appearance, with patchy areas of increased tracer uptake noted in patients with multiple myeloma, aplastic anemia, and myelodysplastic syndrome. Collectively, these data suggest that FLT-PET imaging is a sensitive tool for evaluating overall marrow recovery after HSCT, and that residual FLT activity as well as its overall distribution pattern after transplant could be a useful tool for monitoring for early disease relapse.

Importantly, however, none of these publications evaluated allogeneic transplant patients and none correlated FLT-PET imaging results with the subsequent development of GVHD, graft failure, or disease relapse. Furthermore, none have attempted to correlate FLT-PET results with simultaneous MRI findings which could also be used to predict engraftment success after transplant.

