2.4 Secondary Endpoints

- 2.4.1** The overall FLT-PET bone marrow signal will be defined as the average maximum FLT SUV within the vertebrae, pelvis, and bilateral femurs measured on transplant day +60. Complete donor reconstitution will be defined as chimerisms $\geq 95\%$ within the CD3 and unfractionated compartments on bone marrow biopsy/aspirate obtained on transplant day +100
- 2.4.2** The overall FLT-PET signal within host secondary lymphoid tissue will be defined as the average maximum FLT SUV within the spleen, cervical lymph nodes, axillary lymph nodes, inguinal lymph nodes, and mesenteric lymph nodes

on transplant day +25. Acute GVHD incidence will be diagnosed either clinically or preferably pathologically within any target organ by transplant day +100.

- 2.4.3** The overall FLT-PET signal within recipient secondary lymphoid tissue (average maximum FLT SUV within the spleen, cervical lymph nodes, axillary lymph nodes, inguinal lymph nodes, and mesenteric lymph nodes) and the bone marrow (average maximum FLT SUV within the vertebrae, pelvis, bilateral femurs) in autologous transplant recipients will be compared to the corresponding overall FLT-PET signals from allogeneic transplant recipients on transplant days +25 and +60.
- 2.4.4** Transfusion independence will be defined as not having received a packed red blood cell (PRBC) or platelet transfusion within the 7 days preceding the day +35 or the day +100 time point
- 2.4.5** Bone marrow cellularity will be defined in a dichotomous manner as either hypocellular or normocellular/hypercellular based on the bone marrow pathology report from the day +35 and day +100 bone marrow biopsies.
- 2.4.6** The average FLT SUV in the vertebral column will be compared to the quantitative T1 and Diffusion Weighted Imaging (DWI) signals in the vertebral column by MRI. The average FLT SUV in the pelvis will be compared to the quantitative T1 and Diffusion Weighted Imaging (DWI) signals in the pelvis by MRI. The average FLT SUV in the bilateral femurs will be compared to the quantitative T1 and Diffusion Weighted Imaging (DWI) signals in the bilateral femurs by MRI.

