3.0 PATIENT ELIGIBILITY

3.1 Inclusion Criteria

- 3.1.1** Patients undergoing allogeneic bone marrow transplant for acute myeloid leukemia (AML), acute lymphoblastic leukemia (ALL), or myelodysplastic syndrome
- 3.1.2** Allogeneic transplant patients receiving either a fully myeloablative or reduced intensity chemotherapy +/- total body irradiation (TBI) conditioning regimen are eligible.
- 3.1.3** Allogeneic transplant patients receiving stem cells from a matched related, matched unrelated, mismatched unrelated, mismatched related (including haplotype matched) donors are eligible
- 3.1.4** Allogeneic transplant patients must be in a complete morphologic remission prior to transplant
- 3.1.5** Patients undergoing autologous bone marrow transplant for multiple myeloma
- 3.1.6** Myeloma patients must have achieved at least a very good partial remission prior to transplant and exhibit fewer than 10% plasma cells in their pre-transplant marrow biopsy
- 3.1.7** ≥ 18 years of age
- 3.1.8** Able to provide informed consent
- 3.1.9** Negative urine pregnancy test in women of child-bearing potential

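### The autologous arm cannot show how much of the allogeneic FLT signal is allo-antigen driven, because disease is completely confounded with transplant type; the contrast should be stated as descriptive

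*Combined protocol and SAP*

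**What the plan says.** The purpose of the autologous arm is stated three times. The synopsis (1.1) is the strongest, and says the arm is meant to establish the following: "how much of the FLT signal observed after allogeneic transplant is unique to that population and the result of allo-antigen driven T cell expansion". Section 8.1 is softer and says these patients "help elucidate how much of the FLT signal in allogeneic HSCT patients is related to allo-antigen driven T cell proliferation". Section 1.1.1 gives the reasoning: autologous recipients have no alloreactivity and no GVHD, so they show what the signal looks like without it.

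On size, "3 autologous and 12 allogenic recipients will be recruited".

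On who is compared, section 3.1 admits for the allogeneic arm "Patients undergoing allogeneic bone marrow transplant for acute myeloid leukemia (AML), acute lymphoblastic leukemia (ALL), or myelodysplastic syndrome", and for the comparator "Patients undergoing autologous bone marrow transplant for multiple myeloma". Allogeneic patients must be in complete morphologic remission. Myeloma patients need at least a very good partial remission and fewer than 10% marrow plasma cells. For conditioning, "Allogeneic transplant patients receiving either a fully myeloablative or reduced intensity chemotherapy +/- total body irradiation (TBI) conditioning regimen are eligible". The autologous regimen is described only in general terms, as very high-dose chemotherapy (1.1.1).

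On analysis, endpoint 2.4.3 says the autologous marrow and lymphoid signals "will be compared to the corresponding overall FLT-PET signals from allogeneic transplant recipients on transplant days +25 and +60". Section 8.3.1 names Wilcoxon rank-sum tests for group comparisons. No matching, stratification, adjustment or limit on interpretation is given for this contrast, and 8.2 gives no power figure for it.

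**The concern.** A comparator supports attribution only if it differs from the index group in the factor of interest and is otherwise similar. Here alloreactivity changes together with the underlying disease, the remission requirement and, as far as the documents show, conditioning. A difference in FLT signal could come from any of these, and so could the absence of one.

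Objective 2.2.3 could therefore credit a disease or conditioning difference to T-cell expansion. Section 8.2 says the pilot's results will be used to power a larger study, so a misattributed difference could carry forward into that design.

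**Working it through.** **1. Reproduce the plan's own figures.** Section 8.2 gives 80% power for the allogeneic comparisons at a one-sided 0.10 level. Noether's formula is power = Φ(√(12·c·(1−c)·N)·|P−0.5| − 1.2816), where c is the fraction in one group and P is the probability that a value in one group exceeds a value in the other.
- 6 v 6, P = 0.854: √(12·0.25·12) = 6; 6·0.354 − 1.2816 = 0.842; power 80.0%.
- 7 v 5, P = 0.87: √35 = 5.916; 5.916·0.37 − 1.2816 = 0.907; power 81.8%.

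Both agree with the plan to within 2 points. Neither covers the autologous contrast.

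**2. Is disease separable from transplant type?** The design has four possible cells:

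| | Myeloma | AML/ALL/MDS |
|---|---|---|
| Autologous | 3 | 0 |
| Allogeneic | 0 | 12 |

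Two of the four cells are empty by eligibility. An indicator for disease group equals the indicator for transplant type in every patient, so no adjustment or stratification of these data can separate them. More autologous myeloma patients would not help. At 12 v 12 the P detectable with 80% power falls to about 0.75 (Noether), but the empty cells remain.

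**3. What can 3 v 12 detect?** The plan states no level for this contrast, so I carry over the one-sided 0.10 from 8.2.
- Noether: √(12·0.2·0.8·15) = √28.8 = 5.367; P = 0.5 + 2.123/5.367 = 0.896.
- Exact rank-sum test, simulated under a normal shift: the test rejects when U is at least 28 of 36 (attained level 0.090). 80% power is reached at P of about 0.86, a shift of about 1.5 SD.
- Smallest possible one-sided p: 1/C(15,3) = 1/455 = 0.0022, so significance is attainable.
- Precision of the mean difference: SE = √(1/3 + 1/12) = 0.645 SD. The 95% half-width is 2.160·0.645 = 1.39 SD (t, 13 df, common SD).

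**4. How often would a pure confounder give a positive test?** Assume no allo-immune effect, and a disease or conditioning shift of d SD toward a higher allogeneic signal. Then P = Φ(d/√2). The test is the exact one-sided 0.10 test, 3 v 12.

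| Assumed d | P | Rejection rate |
|---|---|---|
| 0.5 SD | 0.638 | 27% |
| 1.0 SD | 0.760 | 54% |
| 1.5 SD | 0.856 | 79% |

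The documents do not give the size or the direction of such a shift, so this table shows a range and not an estimate. A shift the other way would mask a real allo-immune effect.

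**5. Does the analysis answer the question of amount?** A rank-sum test gives a p-value on ordering. It does not return the share of the signal due to any cause.

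**The case against.** The strongest defence is that this is a declared pilot and the contrast is a secondary objective. Section 8.1 claims only a contribution to understanding, and both primary comparisons are made within the allogeneic arm. All of that stands and limits the severity. It does not rescue the synopsis, which promises to determine the amount.

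The conditioning argument is also incomplete. Reduced intensity and TBI are named only for allogeneic patients, but the autologous regimen is not specified. The documents show an absence of matching and do not fully describe the difference. The confounding by disease needs no such inference.

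Three stronger readings are tempting, and the documents do not support them.

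- *Residual myeloma foci are likely to raise the autologous marrow signal and hide a difference.* Section 1.1.2 does report "patchy areas of increased tracer uptake noted in patients with multiple myeloma", but the same sentence lists myelodysplastic syndrome, an allogeneic-arm disease, and it concerns active disease imaged before therapy. The same section describes 16 myeloma or lymphoma patients after autologous transplant whose marrow uptake was fairly uniform. A masking focus is possible but not shown to be likely.
- *Pooling all 12 allogeneic patients wastes power compared with using only those with GVHD.* This depends on the signal assumed in patients without GVHD. Take 4 patients with GVHD at P = 0.854 against autologous. Pooled power is then 20% if the other 8 have no extra signal (P = 0.5), 51% at P = 0.70 and 78% at P = 0.854, against 53% for 3 v 4. Section 1.1.1 says alloimmune responses also drive the graft-versus-leukemia effect, so some signal without GVHD is plausible.
- *The arm is too small to show anything.* By the exact test, 3 v 12 has 80% power at P of about 0.86, close to the 0.854 the plan uses for 6 v 6. The main defect is attribution, which a larger arm of the same kind would not cure.

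**Conclusion.** The concern holds as a limit on interpretation. The design makes disease completely collinear with transplant type, remission requirements differ, and conditioning is not matched. The planned test therefore cannot attribute a difference to allo-antigen driven expansion or say how much of the signal it explains. This conclusion follows from the eligibility criteria alone.

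The sizes rest on assumptions. The false-attribution rates of 27%, 54% and 79% assume shifts of 0.5, 1.0 and 1.5 SD, normal data with equal variance, and the one-sided 0.10 level borrowed from 8.2. The detectable P of 0.86 to 0.90 depends on whether the exact test or Noether's approximation is used.

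The severity is low: one secondary objective is affected, and the remedy is wording and presentation.

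**What to change.** Keep the enrolment as planned and make three changes.

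1. In 1.1, 1.1.1 and 8.1, describe the autologous contrast as descriptive, and state that it cannot separate alloreactivity from disease, remission status or conditioning.
2. In 2.2.3 and 2.4.3, report individual values for autologous, allogeneic without GVHD and allogeneic with GVHD patients, at both scans and for both tissues. Add the autologous–allogeneic difference with its interval, for example a Hodges–Lehmann shift to accompany the rank-sum test.
3. In 8.3.1, state that no p-value from this contrast will be read as evidence of T-cell expansion.

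The three-group display does not remove the confounding, since autologous v allogeneic with GVHD is still myeloma v leukemia or MDS. Its value is to let readers see the data without an attribution built in.

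Regional mean SUV and a flag for focal marrow lesions in autologous patients would be optional. They are not shown to be collected already: Appendix B has one unlabelled SUV per region, and the focal assessment in 2.2.8 covers allogeneic recipients only.

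The cost is a few sentences and one table. The downside is a weaker stated claim for the autologous arm.

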8.2 Sample Size and Accrual

This is a pilot study to gather preliminary data, and the results from this study will be used to power a future larger R01. However, we will have power to detect large differences between groups as follows. For power calculation, the null hypothesis is that there will be no difference in the FLT bone marrow signal between those allograft patients demonstrating incomplete and complete donor reconstitution on their restaging marrow biopsies, and no difference in the FLT signal within secondary lymphoid tissues between patients with and without acute GVHD.

Complete Donor Reconstitution:

Considering only the 12 allogeneic patients, we will compare the mean FLT bone marrow signal between those with and without complete donor reconstitution. In general we would expect approximately 50-70% of our patients overall to achieve complete donor reconstitution in both the unfractionated and CD3 enriched compartments by transplant day +30.

Assuming equal number of patients with/without Complete Donor Reconstitution:

A sample size of 6 in each group will have 80% power to detect a probability of 0.854 that an observation in the Complete Donor Reconstitution group is less than an observation in the non-Complete Donor Reconstitution group using a Wilcoxon (Mann-Whitney) rank-sum test with a 0.100 one-sided significance level.

Assuming unequal number of patients with/without Complete Donor Reconstitution:

A total sample size of 12 will have 80% power to detect a probability of 0.87 that an observation in the Complete Donor Reconstitution group (n=7) is less than an observation in the non-Complete Donor Reconstitution group (n=5) using a Wilcoxon (Mann-Whitney) rank-sum test with a 0.100 one-sided significance level.

Graft Versus Host Disease:

Considering only the 12 allogeneic patients, we will compare the mean FLT signal within secondary lymphoid tissues in those patients who develop acute GVHD versus those who do not based on the criteria described previously. In general we would expect that approximately 30-40% of our patients will develop some degree of acute GVHD (any site and any clinical grade) by transplant day +100

A sample size of 6 in each group will have 80% power to detect a probability of 0.854 that an observation in the non-GVHD group is less than an observation in the GVHD group using a Wilcoxon (Mann-Whitney) rank-sum test with a 0.100 one-sided significance level.

